1.3 Eligibility screening

Eligibility for the trial is assessed at an initial screening visit, then further assessed at the baseline visit.

1.3.1 Inclusion criteria

1. Initiated on ART for at least 6 months
2. Clinically significant depression symptoms (scoring at least 10 on the Patient Health Questionnaire-9)
3. Viral non-suppression in past two months per local clinical standard (VL>1000 copies/mL) assessed through local clinic or study procedure testing
4. Able to provide informed consent (including being willing for the study team to access medical records for the purpose of this protocol)
5. If prescribed antidepressants, on a stable regimen and dose for at least 2 months

1.3.2 Exclusion criteria

1. Unable or unwilling to provide informed consent
2. Active major mental illness (e.g. untreated psychosis or mania, actively suicidal), major untreated or undertreated mental illness or advanced physical disease or severe cognitive impairment (assessed using the psychosis module of the MINI, the PHQ-9, and the International HIV dementia Scale) which would interfere with engagement in PST-AD.
3. Has already received PST or CBT for depression
4. Less than 18 years of age

1.4 Method of allocation of groups

Patients will complete baseline measures after providing informed consent to take part in the trial. Approximately two weeks after baseline assessments are complete, eligible individuals will be randomised to one of the trial arms using a variable block randomisation procedure. Randomisation will be done at the patient level in a 1:1 ratio and will be stratified on site (using the Sealed Envelope schema coordinated via REDCAP).

1.5 Duration of the treatment period

For the TENDAI group, 6 sessions will be delivered, one per week, with one booster session in week 12 post-randomisation. For the EUC group, there are 3 adherence counselling sessions. Providers of EUC are all trained in the WHO mhGAP guidelines for depression care and are free to follow this as per their preference and training. The antidepressant drug Fluoxetine is available for TENDAI providers and for EUC providers to prescribe.

1.6 Frequency and duration of follow-up

Participants will complete baseline measures prior to randomisation. Follow up measures will be completed at 4, 8 and 12 months post randomisation. Please see section 5 SCHEDULE OF ASSESSMENTS AND MEASURES for details and the data collection schedule.

1.7 Visit windows

An overview of the trial schedule is shown in [Figure 1. Trial design flow diagram](#).

Randomisation will be done after completing baseline measures which are listed in section 5 SCHEDULE OF ASSESSMENTS AND MEASURES. There is no specified time window between the baseline visit and randomisation.

Treatment should be initiated as early as possible after randomisation. There is no specified time window. For the TENDAI group, sessions should be provided weekly (any day) between weeks 1 to 6 following randomisation, plus a booster session in week 12 following randomisation.

Follow-up visits should be no earlier than 30 days prior to the expected visit date, no later than 60 days after the expected visit date for 4 and 8 month follow up assessments, and no later than 120 days after the expected visit date for the final 12 month follow up. Visit window data will be summarised (see section 3.1.4.1); data collected outside the visit windows will still be used.

1.8 Measures

1.8.1 Baseline measures

The following measures are recorded at baseline (see Section 5, Table 5.1): MINI (depression), PHQ-9 (depression), PCL-5 (PTSD), medications used, recent or current pregnancy, current comorbid illness, Alcohol Use Disorders Identification Test (AUDIT), CD-4, viral load (blood plasma), DBS for ART detection, Self-report adherence (AQ), pharmacy refill adherence, mode of HIV transmission, depression treatment plus non-study therapy, Drug Use Disorders Identification Test (DUDIT), Social support (SS), HADS anxiety subscale, Adherence Self-Efficacy scale (ASES), Barriers to AntiRetroviral Adherence (BARTA), Problem Solving Skills subscale (PSSS), HIV related dementia scale (IHDS). COVID-19 measures were also added in March 2021.

Sociodemographic measures recorded at baseline include: age, sex, relationship status, educational history and level attained, income, main job, household assets. See section 2.2 for a list of the baseline variables that will be described in the primary paper.

Health economic outcomes are also recorded; CSRI and EQ5D3L.

1.8.2 Primary outcome measure

The primary outcome is viral suppression (<1000 copies/mL) at 12 months follow-up. The recorded viral load will be coded into a binary not suppressed/suppressed variable. Those missing viral load data where the medical or death records indicate a likely high viral load or AIDS related death will also be considered to be not suppressed – see also section 3.1.1. Viral suppression will be taken from the result recorded by the hospital if recorded within the 30 days prior to the 12 month post-randomisation visit date or will be assessed from a blood sample (plasma) collected by the trial team at the 12 month post-randomisation visit.

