1.2 Trial design including blinding

A 12-month parallel arm randomised controlled trial of the TENDAI intervention on depression and ART adherence in adult patients living with HIV compared with enhanced usual care (EUC). Participants will be randomised 1:1 to 12-months treatment with either TENDAI or EUC. Randomisation, which will be stratified by site as the study will now take place in the Chitungwiza Central Hospital as well as the Marondera Provincial Hospital, will be conducted using a variable block randomisation schema (using Sealed Envelope) coordinated through the trial REDCap database. Only the Zimbabwean site Project Manager and the trial Database Manager have the ability to randomise participants. Eligibility for randomisation is confirmed on a weekly cross-site call, which involves the Zimbabwe study team, the study Principal Investigators, and study Clinical supervisors. The principal investigators, local and London programme managers, data manager and interventionists are unblinded. Blinded independent assessors will administer the PHQ-9, EQ-5D-3L, self-report adherence questionnaires at follow-up. The senior statistician will be fully blinded, and the junior statistician will be unblinded.

Figure 1. Trial design flow diagram

Schematic diagram of flow of participants (potential and actual) through the pre-trial assessment and trial. Please see the CONSORT diagram (Figure 2) for detail on how this will be reported.

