1.9 Sample size estimation

A sample size of 290 participants will provide 85% power to detect an absolute difference of 20% or more in achieving viral suppression (e.g. 45% in the EUC arm vs. 65% in the intervention arm) at 12-months follow-up. This is based on a two-sided Fisher's exact test with $\alpha = 0.05$ and allowing for 20% attrition. Pilot data showed a larger difference between arms (50% in the EUC arm vs. 75% in the intervention arm), suggesting this should be a conservative sample size estimate. For the secondary outcomes, this sample size will allow detection of an effect size of 0.37 or greater on the continuous depression scale (based on $\alpha = 0.05$, a two-sided test of difference between two independent means and the same level of attrition). The sample size will also provide 90% power to detect a 20% difference in the proportion with $\geq 90\%$ adherence as was seen in our pilot data (also Fisher's exact test, $\alpha=0.05$ and 20% attrition). This is based on our pilot data, national data (Dube et al) and other research (Ciesla et al, Safran et al).

2. Data analysis plan – Data description

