3.1 Main analysis of treatment differences

The main statistical analyses will follow the intention to treat principle as much as possible. The senior statistician will remain fully blind until an initial draft of the primary analysis report is complete and needs to be checked. The trial

statistician will be unblinded. Group difference estimates between TENDAI and EUC and associated 95% confidence intervals will be reported from models appropriate to the measurement schedules and nature of the outcome in question, i.e. depending on whether the outcome is continuous or categorical. The models that will be used are outlined in the following sections. Where the outcome variable is recorded at baseline it will generally be included in the analysis model as a covariate unless stated otherwise. The significance level for the difference between TENDAI and EUC on the primary outcome will be 5% (two-sided). This significance level will also be used for the secondary outcomes, but the reader will be alerted regarding the impact of multiple testing.

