3.1.1 Analysis of primary outcome

The viral load data will be coded into a binary variable as follows: <1000 copies/mL (suppressed) or ≥1000 copies/mL (not suppressed), please also see Appendix 1. Where the viral load data are missing at 12 months and the individual has died, the data will be left missing unless it is apparent from medical or death records that the person died due to high viral load or death was clearly AIDS related, in which case we will code them as not suppressed. The odds ratio at 12 months (and associated 95% CI) for <1000 copies/mL for TENDAI vs EUC will be estimated using a logistic regression model with the 12 month measure as the dependent variable, and trial arm as the independent variable, as well as the site stratification variable. We will fit two models, the one just described excluding baseline log viral load, and another including this as an independent variable, so will present odds ratio estimates both marginal and conditional with respect to baseline viral load. Moderation of treatment effects by sex will be assessed in these two final model backgrounds as outlined in Section 3.1.3.

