If there are post-randomisation variables that predict missing outcome data, we will impute a number of datasets equal to the percentage missing data in the primary viral load outcome (Dong and Peng) or 50 datasets (whichever is higher). As well as the relevant variables from Sections 3.1.1 and 3.1.2, the imputation model will include all baseline and post-randomisation variables we find to predict missing outcome data and the putative moderating variable sex, imputing the trial arms separately as recommended by Thomas et al when moderation analysis is planned. We will endeavour to construct the imputation models as described, but if not viable, we may need to consider a set of simpler imputation models (i.e. when imputing with interaction terms we may need to remove some other variables from the imputation model). Where MI is used, we will produce estimates from both the complete case and MI data and include both in the statistical report, with the latter being the main estimates reported in the primary publication. If there are no post-randomisation variables that predict missing outcome data, but there are baseline variables predictive of missing data, these will be included in the non-logistic primary and secondary outcome analysis models (i.e. PHQ-9, self-report adherence, log viral load).

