3.1.5 Sensitivity analyses

3.1.5.1 Viral load primary outcome assumptions

We will undertake two sensitivity analyses on the primary binary viral load outcome, repeating the analysis described in Section 3.1.1:

- 1) excluding the individuals that died with missing viral load and were coded as non-suppressed (died due to high viral load or death was clearly AIDS related),
- 2) assuming the medical/death data were incorrect and coding these individuals (that died with missing viral load and were coded as non-suppressed) as virally suppressed.

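### SAP 1.8.2 and 3.1.1 give conflicting rules for recoding a missing primary outcome as not suppressed, and the wider rule has no blinded judgement or sensitivity analysis behind it

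*SAP*

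**What the plan says.** The primary outcome is viral load below 1000 copies/mL at 12 months. Two SAP sections say what to do when the value is missing.

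- **SAP 1.8.2** treats as not suppressed "Those missing viral load data where the medical or death records indicate a likely high viral load or AIDS related death". It then points the reader to 3.1.1.
- **SAP 3.1.1** speaks only of participants who died. For them "the data will be left missing unless it is apparent from medical or death records that the person died due to high viral load", or unless the death was clearly AIDS related. Only then are they coded as not suppressed.

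The protocol sections on outcomes (12), data collection (18a) and missing data (20c) contain no recoding rule, so they cannot settle which one applies.

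**Blinding (SAP 1.2 and 3.1).** The principal investigators, programme managers, data manager and interventionists are unblinded. For the statisticians: "The senior statistician will be fully blinded, and the junior statistician will be unblinded". The senior statistician stays blind until a first draft of the primary analysis report needs checking. Nobody is named to judge the records, and no criteria are given.

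**Sensitivity analyses (SAP 3.1.5.1).** There are two. The first is "excluding the individuals that died with missing viral load and were coded as non-suppressed"; the second codes those same people as suppressed.

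**Multiple imputation (SAP 3.1 and 3.1.4.5).** It is considered only if a post-randomisation variable predicts missingness and at least ten percent of outcome data are missing. If it is triggered, "we will impute a number of datasets equal to the percentage missing data in the primary viral load outcome", or 50 if that is higher, and the imputed result becomes the main published estimate. Nothing says how deaths are treated in the imputation.

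**The concern.** Two statisticians working from this SAP could build different primary datasets. One, following 1.8.2, would search the records of everyone without a 12-month value and code as failures those who look likely to have a high viral load. The other, following 3.1.1, would touch only deaths.

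The wider rule works in one direction: records pointing to failure create a failure, while records pointing to suppression leave the value missing. A hospital viral load counts as the outcome only if recorded within the 30 days before the 12-month visit. An older high result in the chart could therefore be read as a likely high viral load and become a failure; an older low result has no effect.

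Because the judgement is open and need not be blind, it is a route by which knowledge of the arm could enter the sole primary endpoint. Any living participant recoded in this way falls outside both planned sensitivity analyses. Deaths that are not recoded also have no stated strategy: they either drop out of the logistic model or, if the imputation conditions are met, could be given an imputed viral load status.

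**Working it through.** **1. The two rules side by side**

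| | SAP 1.8.2 | SAP 3.1.1 |
|---|---|---|
| Who can be recoded | anyone with a missing value | only those who died |
| Standard of evidence | likely high viral load, or AIDS-related death | apparent from the records, or clearly AIDS related |
| Direction | to not suppressed only | to not suppressed only |
| Covered by 3.1.5.1 | only those who died | all who are recoded |

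The population and the standard of evidence both differ, and the cross-reference does not say which section governs.

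**2. The plan's own figure.** Inputs from SAP 1.9: "A sample size of 290 participants will provide 85% power" for "45% in the EUC arm vs. 65% in the intervention arm", two-sided Fisher's exact test, alpha 0.05, 20% attrition. Evaluable per arm = 290 × 0.8 / 2 = 116. Full enumeration of the Fisher test gives a power of 85.0%, so the stated figure reproduces. This point does not alter it.

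**3. How many could be affected.** Planned missing outcomes: 0.20 × 290 = 58, or 29 per arm. Literal 1.8.2 could reach any of them whose records suggest a high viral load; 3.1.1 reaches only deaths. The documents give no count for either, so the recode numbers below are assumptions.

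**4. Effect of recoding at the design rates.** Start from 52/116 (44.8%) on EUC and 75/116 (64.7%) on TENDAI. Recoding k participants in an arm adds k failures to it:

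OR = [75 / (41 + k_T)] / [52 / (64 + k_E)]

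| Recodes (EUC, TENDAI) | EUC | TENDAI | OR (95% CI) |
|---|---|---|---|
| 0, 0 | 52/116 | 75/116 | 2.25 (1.33 to 3.82) |
| 10, 10 | 52/126 | 75/126 | 2.09 (1.27 to 3.46) |
| 10, 0 | 52/126 | 75/116 | 2.60 (1.55 to 4.38) |
| 0, 10 | 52/116 | 75/126 | 1.81 (1.09 to 3.02) |
| 29, 29 | 52/145 | 75/145 | 1.92 (1.20 to 3.07) |

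**5. Near the significance boundary.** 52/116 against 68/116 gives Fisher p = 0.049. Two recodes on TENDAI only (68/118) give p = 0.067. Two on EUC only (52/118) give p = 0.027.

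**6. No true difference.** Take the same true rate in both arms, between 45% and 65%, 116 observed per arm and a pooled z-test at two-sided 5%. The chance of a significant result favouring TENDAI is:

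| Recodes (EUC, TENDAI) | Chance |
|---|---|
| 0, 0 | 2.4% to 2.8% |
| 3, 0 | 3.7% to 4.4% |
| 5, 0 | 4.9% to 6.0% |
| 10, 0 | 8.2% to 12.3% |
| 10, 5 | 3.8% to 4.9% |

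By symmetry, recoding only on TENDAI would inflate results favouring EUC to the same extent. Imbalance between the arms does the damage, more than the number recoded.

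**The case against.** The best reply is that the conflict is one of drafting. Section 1.8.2 is a summary that refers to 3.1.1, the operative section. SAP 3.1.5.1 describes the recoded people as having died, and the SAP's change log likewise speaks of an assumption for deaths. That probably reflects the intention. It does not remove the problem, because 1.8.2 is the section that defines the primary outcome and its wording still includes the living.

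Several stronger readings are tempting, and the documents do not support them.

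- **That record review would work against a particular arm.** A reader might infer this from the extra TENDAI sessions. But protocol 11a says the TENDAI counsellors do not provide routine care and work in a separate building, while EUC counselling is given by facility staff. Nothing says TENDAI session notes enter the medical record, and EUC counselling could be the better documented there. The direction by arm is unknown.
- **That dead participants would be imputed as if alive.** Imputation needs both conditions set out in SAP 3.1. Otherwise these deaths are excluded, and complete-case estimates are produced even when imputation is used. The most that can be said is that they could be imputed.
- **That the planned sensitivity analyses are useless.** For recoded deaths, exclusion and coding as suppressed, set against the main analysis, span the full range. The gap is everyone else with a missing outcome.
- **That every death should count as failure in the main analysis.** This would change the protocol's endpoint to a composite of survival and suppression. SAP 3.1.1 infers a high viral load from the cause of death; it does not treat death itself as failure.

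It is also fair that 20% attrition is a planning allowance. Protocol 20c expects considerably less, and protocol 18b does not expect mortality to be a significant source of attrition.

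**Conclusion.** Wrong as written: the SAP holds two incompatible rules for the primary endpoint. The literal wording of 1.8.2 permits one-directional recoding of living participants, with no blinded judgement and no sensitivity analysis to expose its effect. Because few deaths are expected, this reach to the living is the part most able to change the result.

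The size cannot be stated from the documents. If recoding is balanced it is modest, even at ten per arm. If it is one-sided it can matter: two recodes can move a borderline p-value across 0.05, and ten can take a design-size odds ratio down to 1.81 or up to 2.60. These figures assume 116 observed per arm, unadjusted two-by-two tables and recode counts chosen for illustration. They show what the open rule allows and do not forecast what will happen.

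**What to change.** 1. Amend SAP 1.8.2 to match 3.1.1: recode only deaths apparently due to high viral load or clearly AIDS related. Living participants without a viral load value stay missing, whatever their records suggest.
2. Have the records judged by someone blind to arm, against written criteria, and lock the decisions before analysis.
3. State in SAP 3.1.4.5 that deaths left missing are not imputed if multiple imputation is used.
4. Keep both analyses in SAP 3.1.5.1 and add three: all missing outcomes set to not suppressed in both arms; a tipping-point analysis that varies the assumed suppression rate among the missing separately by arm; and, as a sensitivity analysis only, all deaths set to not suppressed.

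The cost is a short SAP amendment, a simple form for the record review and a little more analysis work. The protocol endpoint and the sample size do not change. As the trial statistician is unblinded, the amendment should be agreed and dated without reference to outcomes by arm.

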1.8.3 Secondary outcome measures

Secondary outcomes are:

1. Continuous depression score measured using Patient Health Questionnaire (PHQ) at 12 months post randomisation.
2. Adherence using pharmacy refill which will be recorded as a percentage adherence over the past month at 4, 8 and 12 months post randomisation. Adherence will be coded into a binary variable reflecting at least 90% adherence or not – see Section 3.1.2 for more detail.
3. Adherence using self-reported adherence to ART medication using a self report questionnaire scale (Wilson et al) measured at the 4, 8 and 12 months post randomisation visit. See Section 3.1.2 for more detail.
4. Continuous log (base 10) viral load copies/mL at 12 months using hospital records if recorded within the 30 days prior to the 12 month post-randomisation visit date or will be assessed from a blood sample (plasma) collected by the trial team at the 12 month post-randomisation visit.

1.8.4 Mediators of treatment effects

Hypothesised mediators of (a) the effect of TENDAI on depression and adherence outcomes, i.e. social support, PSSS and ASES, are recorded at baseline, 4 8 and 12 months. Hypothesised mediators of (b) the effects of TENDAI on viral suppression, i.e. depression, pharmacy refill, and blood sample measures of adherence are recorded at 4, 8 and 12 months. The social support, PSSS and ASES and dried blood spot measure of adherence that feature only in the mediation analysis will not be summarised in the main paper and so will not be referred to again in this SAP. The depression and pharmacy refill measures of adherence that will be studied as mediators of the effect of TENDAI on viral suppression are also secondary outcomes in the main trial. Mediation will not be reported in the primary trial paper and will not be discussed further in this document.

1.8.5 Moderators of treatment

The effect of the baseline moderator, sex, on the primary outcome of viral suppression, and the secondary outcomes of self-report adherence (Wilson et al) and depression will be tested. Moderation of the treatment effect by sex will be assessed for the main paper, and so methods for this analysis are discussed in this SAP (please see section 3.1.3). Further exploratory moderators household assets (BARTA) and depression severity mentioned in the protocol will be explored in further analyses which are beyond the scope of this SAP.

[figure not shown]
1.9 Sample size estimation

A sample size of 290 participants will provide 85% power to detect an absolute difference of 20% or more in achieving viral suppression (e.g. 45% in the EUC arm vs. 65% in the intervention arm) at 12-months follow-up. This is based on a two-sided Fisher's exact test with $\alpha = 0.05$ and allowing for 20% attrition. Pilot data showed a larger difference between arms (50% in the EUC arm vs. 75% in the intervention arm), suggesting this should be a conservative sample size estimate. For the secondary outcomes, this sample size will allow detection of an effect size of 0.37 or greater on the continuous depression scale (based on $\alpha = 0.05$, a two-sided test of difference between two independent means and the same level of attrition). The sample size will also provide 90% power to detect a 20% difference in the proportion with $\geq 90\%$ adherence as was seen in our pilot data (also Fisher's exact test, $\alpha=0.05$ and 20% attrition). This is based on our pilot data, national data (Dube et al) and other research (Ciesla et al, Safran et al).

2. Data analysis plan – Data description

